- ⁴ A preliminary check of in-/exclusion criteria is recommended at Visit 0 to avoid unnecessary washout procedures in non-eligible patients.
- ⁵ To be performed only if relevant findings at Visit 4/EOT.
- ⁶ Women of child-bearing potential: pregnancy test at Visit 1 and Visit 4/EOT
- ⁷ The patient will be instructed in the use of the RESPIMAT, but patient **should not** inhale from the training inhaler at Visit 2.
- ⁸ Rescue medication as salbutamol is prescribed at visit 0. Rescue medication will be collected and prescribed on subsequent visits by investigators as needed. All rescue medication for the trial to be confirmed to be collected at Visit 4/EOT.
- ⁹ Pre- and post-bronchodilator (400 µg salbutamol) [note: reversibility is not an inclusion criterion], Spirometry measurement; FVC and FEV₁ only.
- ¹⁰ Baseline spirometry measurement FEV₁, FVC, SVC, and IC.
- ¹¹ Morning post-dose spirometry

Proprietary confidential information © 2015 Boehringer Ingelheim International GmbH or one or more of its affiliated companies

- FEV₁ and FVC: 30 min post-morning dose as starting time
- IC and SVC measurement: 60 min post-morning dose as starting time

12
13

Prior to the start of PFTs are performed.

[REDACTED]

14

Patients should wear and measure activity monitor (3-axis accelerator) every day for 2 weeks prior to Visit 2, Visit 3 and Visit 4/EOT.

15

[REDACTED]

16

17

Site staff will telephone the patients 15 days and 8 days prior to the next planned Visit and remind them to wear physical activity monitor every day. An assessment of adverse events and of concomitant therapy should be performed from the last assessment.

18

Trial medication dispensed at Visit 2 should be administrated at clinic at Visit 3 and trial medication dispensed at Visit 3 should be administrated at clinic at Visit 4/EOT. Newly assigned trial medication at Visit 3 should be administered next day of Visit 3.

19

[REDACTED]

20

Refer to [Appendix 10.8. mMRC](#)

21

Training of 6MWT

22

Refer to [Appendix 10.11](#)

23

Training of patient diary at Visit 1. Dispense of the diary at Visit 1, Visit 2 and Visit 3. Reviewing and collection of the diary at Visit 2, Visit 3 and Visit 4/EOT.

TIMING OF PROCEDURES: VISIT1_SCREENING

	Start time					
	-	More than 30 min prior to Pre-dosing PFT	-10 to 0 min prior to administration salbutamol	administration salbutamol (0 min)	10 to 15 min after administration salbutamol	-
Medication washout compliance	X					
mMRC ¹	X					

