3. DESCRIPTION OF DESIGN AND TRIAL POPULATION

3.1 OVERALL TRIAL DESIGN AND PLAN

This is a multi-centre, randomised, double-blinded, active-controlled, 2-way cross over trial to assess the effects of once daily administration of orally inhaled tiotropium + olodaterol FDC 5 µg/5 µg or tiotropium 5 µg (both delivered by the RESPIMAT Inhaler) on pulmonary function (lung hyperinflation), exercise capacity (6-minute walk distance [6MWD]) and physical activities after 6 weeks of treatment in Japanese patients with COPD.

After signing Informed Consent (Visit 0) and completing an initial screening visit (Visit 1) after appropriate stable treatment with LAMA or LABA mono therapy (In case, patients who treated with combination of LABA and LAMA need to be treated at least 3 weeks with only monotherapy component.) and ensuring clinical stability (i.e. no exacerbations), patients will start a 2-week screening period. During the screening visit (Visits 1), they will conduct baseline physical activity assessments (between Visit 1 to Visit 2) and baseline IC (Visit 2) and 6MWT (Visit 1 and Visit 2).

Patients who meet all the inclusion criteria and none of the exclusion criteria will be randomised (1:1 ratio) at Visit 2 into the 2-period 6-week double-blind, cross-over treatment portion of the study, in which they will receive one of two treatment sequences as follows:

Sequence AB; Tiotropium followed by Tiotropium + olodaterol FDC

Sequence BA; Tiotropium + olodaterol FDC followed by Tiotropium

for a total of 12 weeks of treatment (Figure 3.1: 1).

[figure not shown]

Figure 3.1: 1 Trial design

An Interactive Response Technology (IRT) will be used for randomisation to a treatment sequence in this trial and for appropriate re-supply of medication to patients.

In this trial, patients who complete first 6-week treatment period will subsequently start second 6-week treatment period. There is no washout period between each treatment periods.

Pulmonary function testing (PFT) will be conducted at Visit 1, just before (within 10 min) and 10-15 min after inhalation of subltamol for inclusion, at Visit 2 for baseline and at Visit 3 and Visit 4/EOT during the treatment period (30 min post-dosing and 60 min post-dosing)

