5.2 ASSESSMENT OF EFFICACY

5.2.1 Pulmonary Function Testing

These tests will be performed using spirometers (Flowscreen, eResearch Technology GmbH) provided by BI. Spirometers and their use, including daily calibration, must meet ATS/ERS criteria ([P05-12782](#)). Baseline PFT will be conducted at Visit 2. PFT will also be conducted post-dose and before 6MWT (at Visit 3 and Visit 4). Patient will be in a seated position and it is preferable that the same trained individual performs the pulmonary function tests for a given patient.

Baseline IC and SVC measurement (Visit 2) should be done 30 minutes before 6MWT. IC and SVC measurement (at Visit 3 and Visit 4) should also be done 30 minutes before 6MWT, which is on 60 minutes post-dosing. For IC and SVC at least three reproducible measurements should be obtained with a maximum of 5 measurements to be performed. The resting IC and SVC should be recorded as the mean of the two highest acceptable efforts. For additional details on the IC maneuvers, please refer to [Appendix 10.11](#).

Baseline FEV₁ and FVC measurement (Visit 2) should be done 60 minutes before 6MWT. FEV₁ and FVC measurement (at Visit 3 and Visit 4) should also be done 60 minutes before 6MWT, which is on 30 minutes post-dosing. The best of three efforts will be defined as the highest FEV₁ and the highest FVC each obtained on any of three manoeuvres meeting the ATS criteria (to a maximum of five attempts). The highest FEV₁ and the highest FVC will be selected regardless of whether they come from different spirometric manoeuvres or from the same manoeuvre.

If a patient is unable to complete the PFTs during a visit, the CML should be notified as soon as possible. The eCRF will be completed indicating the reason for stopping testing, rescue medication given (if any) and time of rescue medication. Patients who are unable to complete the study visit may leave the clinic only upon instruction from the supervising physician.

Reversibility testing ([P05-12782](#)) for the qualifying PFT at the Screening Visit (Visit 1): the procedure is described in [Appendix 10.5](#). The post-bronchodilator measurements must meet the inclusion criteria specified in [Section 3.3.2](#).

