6.6 HANDLING OF MISSING DATA AND OUTLIERS

Completely missing visits not due to worsening of study disease will not be imputed and will stay as missing, because such missing data are considered as randomly missing data and will be handled in the mixed model repeated measures model.

Completely missing visits/weeks due to the patient discontinuing due to worsening of study disease will be imputed with the baseline value.

It could happen that a patient needed therapy for COPD symptoms at a clinic visit. This therapy was entered on the rescue medication of electronic Case Report Form (eCRF). This may or may not be the rescue medication provided by Boehringer Ingelheim (BI). For purposes of the imputation rules this will be termed “rescue medication” regardless of whether or not it was BI-supplied rescue medication.

For spirometry data, the records which are flagged as “unacceptable” by the vendor (ERT) will be administratively set to missing and treated as randomly missing data for imputation purpose.

The following rules are used for exercise data:

- [REDACTED]
- Measurements of oxygen saturation, blood pressure and heart rate which are missing during recovery will not be imputed.
- [REDACTED]

The following rules will be used for spirometry data which were collected at Visits 2, 3 and 4:

- Since there is only one spirometry measurement at each on-treatment clinic visit, rescue medication use on or before the spirometry measurement or rescue use with unknown time will both result in all spirometry measurements for the visit being set to missing. In these cases the entire visit will be imputed with baseline.
- If spirometry measurements for an entire visit are completely missing because a patient discontinued due to worsening of study disease, then all data for this visit will be imputed with baseline.
- Randomly missing spirometry measurements will not be imputed.

Missing safety data will not be imputed with the exception of missing or incomplete AE dates which will be imputed according to BI guideline 'Handling of missing and incomplete AE dates' (1).

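### The SAP's rescue rule assumes one spirometry measurement per visit, but Visits 3 and 4 have two timed sessions, so rescue between them overwrites valid FEV1 and FVC on a literal reading (minor)

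*SAP*

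**What the plan says.** **SAP 6.6, spirometry rules.** The first bullet begins "Since there is only one spirometry measurement at each on-treatment clinic visit, rescue medication use on or before the spirometry measurement". It adds rescue use at an unknown time and states that these "will both result in all spirometry measurements for the visit being set to missing". It continues: "In these cases the entire visit will be imputed with baseline". The second bullet imputes baseline when a whole visit is missing because the patient discontinued for worsening disease. The third reads "Randomly missing spirometry measurements will not be imputed".

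**Protocol schedule.** Flow chart footnote 11 gives "30 min post-morning dose as starting time" for FEV1 and FVC, and separately "IC and SVC measurement: 60 min post-morning dose as starting time". Section 3.1 lists "30 min post-dosing and 60 min post-dosing" for the treatment-period visits. Section 5.2.1 places FEV1/FVC 60 minutes before the walk test, "which is on 30 minutes post-dosing", and IC/SVC 30 minutes before it. Appendix 10.10 puts IC after FEV1 and FVC. The SAP itself refers to a 60-minute PFT, in item F3.6 of Table 6.2: 1.

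**Rescue on a test day.** Protocol 4.2.1.1 stops the PFTs if rescue is needed, asks for rescheduling where that can be done, and has the clock time of rescue recorded in the eCRF.

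**The concern.** The rule's stated reason does not match the schedule. With two sessions, rescue can come after FEV1/FVC and before IC/SVC, and the rule does not say which session decides whether it applies. Its consequence is written for the whole visit, so on its plain words it discards FEV1 and FVC values that rescue cannot have influenced. It puts in their place a baseline taken before any trial medication (SAP 6.7; Protocol 4.1.4).

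A second, smaller gap concerns IC and SVC. Because testing stops after rescue, the usual result would be an IC that was never taken. The SAP does not say in terms whether such a value counts as lost to rescue (impute baseline) or as randomly missing (leave missing).

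At stake are the handling of two secondary endpoints, and an explicit rule for the primary endpoint and SVC, at a small number of visits.

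**Working it through.** **1. Where the rule is clear and where it is not** (visit not rescheduled)

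| Rescue time | Effect of SAP 6.6 |
|---|---|
| On or before FEV1/FVC | All four parameters imputed with baseline on any reading |
| Between FEV1/FVC and IC/SVC | Depends on the reading (step 2) |
| After IC/SVC | Rule not triggered on any reading |
| Unknown | All four imputed with baseline |

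**2. Rescue between the sessions**

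| Reading | FEV1/FVC (obtained before rescue) | IC/SVC |
|---|---|---|
| A. Visit-level, as worded | Overwritten with baseline | Imputed with baseline |
| B. By parameter | Kept | Imputed with baseline |
| C. Only the 30-minute session counts | Kept | Kept if taken after rescue; unclear if not performed |

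A and B agree on IC and differ on FEV1/FVC. C differs on IC but is strained: it makes the trigger a session that does not contain the primary endpoint. If IC was not performed, the other rules do not settle it. FEV1/FVC exist, so the visit is not completely missing. The second bullet needs discontinuation for worsening disease. The third applies only if the loss is called random.

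**3. Planning figures** (Protocol 7.7: difference 0.1 L, SD 0.41 L, 90% power, two-sided 0.05, n = 180). An exact one-sample t calculation gives 179 (171 for SD 0.40, as stated), and power at 180 is 90.2%, so the plan's figures reproduce. Planned standard error = 0.41/√180 = 0.0306 L.

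**4. Size.** Let q be the share of visits with rescue between sessions and no rescheduling (F = combination, T = tiotropium), δ the true treatment difference and g the tiotropium gain over baseline. The documents give no q, no g and no δ for FEV1/FVC, so these are assumptions. With q of 0.5% to 2%, 360 planned records (180 × 2) give 1.8 to 7.2 affected visits.

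Means after baseline imputation: combination (1 − qF)(g + δ); tiotropium (1 − qT)g. Subtracting δ from their difference:

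shift = −qF·δ + (qT − qF)·g

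With equal rates g drops out and shift = −q·δ. If values left missing are missing at random, leaving them missing gives no shift.

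| q (equal) | IC, δ = 0.10 L: imputed minus left missing | FEV1/FVC, δ = 0.05 to 0.15 L: overwritten minus kept |
|---|---|---|
| 0.5% | −0.0005 L | −0.00025 to −0.00075 L |
| 1% | −0.001 L | −0.0005 to −0.0015 L |
| 2% | −0.002 L | −0.001 to −0.003 L |

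Largest IC entry: 0.002/0.0306 = 6.5% of the standard error. At q = 2% the expected IC difference is 0.098 L and power is 89.1% (SD held at 0.41 L).

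Unequal rates, with g = 0.1 to 0.3 L assumed for every parameter:

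- qT = 1%, qF = 2%: IC −0.02 × 0.10 − 0.01 × g = −0.003 to −0.005 L; FEV1/FVC −0.002 to −0.006 L.
- qT = 2%, qF = 1%: IC −0.01 × 0.10 + 0.01 × g = 0 to +0.002 L; FEV1/FVC −0.0005 to +0.0025 L.

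**The case against.** The best defence is that the premise has an ordinary meaning that is true: each parameter is measured once per on-treatment visit, with no serial time points, so no carry-forward or interpolation rule is needed. That is probably the intent. It does not rescue the text, because the consequence is written for all spirometry and the entire visit, which a by-parameter rule would not say.

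A reader might infer that the trigger is simply undefined for the primary endpoint. The documents do not support that. Readings A and B both send an IC preceded by rescue to baseline, F3.6 labels the 60-minute PFT as the primary-endpoint recording, and an IC not performed can be taken as part of the visit that is imputed. What stands is that this last step is implied, not stated. Protocol 7.5 does not supply it either: it mentions sponsor standard approaches and leaves the detail to the SAP.

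It is also fair that such visits will be rare. They need rescue in a nominal 30-minute gap soon after supervised dosing, at a visit that could not be rescheduled. Blinded review would probably see them, since SABA use within 8 hours of a PFT breaches the washout in Protocol 4.2.2.1 and item D1 sends improper washout to the blinded meeting. But D1 governs only exclusion from the PPS, not imputation in the FAS.

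**Conclusion.** The point stands as a minor one. The premise in SAP 6.6 conflicts with the protocol schedule and with the SAP's own F3.6. For rescue between the sessions at a visit that is not rescheduled, the literal rule overwrites valid pre-rescue FEV1 and FVC with a pre-dose baseline. For the primary IC the natural readings impute baseline, and only the not-performed case needs an express statement.

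With assumed equal rates of 0.5% to 2%, the choice moves the IC contrast by no more than 0.002 L and the FEV1/FVC contrast by no more than 0.003 L. A reader might take the larger IC shift of 0.005 L, about 16% of the standard error (0.005/0.0306), as the expected size. It needs twice the rate under the combination (2% against 1%) and a 0.3 L tiotropium gain in IC over baseline. The documents give neither, so it is an outer bound under stated assumptions. Nothing here suggests that the primary conclusion is at risk.

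**What to change.** Delete the one-measurement premise and apply the planned rule by parameter:

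- Rescue on or before the actual FEV1/FVC time: FEV1 and FVC are set to missing and imputed with baseline.
- Rescue on or before the actual IC/SVC time, or IC/SVC not performed because testing stopped after rescue: the same for IC and SVC.
- Values obtained before a recorded rescue time are kept.
- The rule for unknown rescue times is unchanged.

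The cost is a few lines of SAP text and minor programming before unblinding. No change to visit procedures is involved. The rescue clock time is recorded (Protocol 4.2.1.1 and 5.2.1), and the automatic F3.6 check implies that the 60-minute PFT time is in the database. The documents do not state this for the 30-minute session, so the sponsor should confirm that its time is held as well.

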4.2 CONCOMITANT THERAPY, RESTRICTIONS, AND RESCUE TREATMENT

4.2.1 Rescue medication, emergency procedures, and additional treatment(s)

4.2.1.1 Rescue Medication

Administration of rescue medication can occur at any point during the trial as deemed necessary by the patient or the investigator. Salbutamol will be prescribed as rescue medication in the trial site; only the salbutamol prescribed in the trial site is allowed for rescue medication use. If the patient requires rescue medication during the pulmonary function test (PFT) days (Visits 1, 2, 3, and 4), the PFTs will be discontinued. The visit should be rescheduled if possible. The medication used, route and 24-hour clock time of administration will be recorded on the Rescue Medication eCRF page.

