Miscellaneous	Other investigational drugs (see exclusion criterion)	NOT permitted	NOT permitted	NOT permitted	NOT permitted
	Cromolyn sodium / nedocromil sodium (if prescribed for non-asthma condition)	Permitted	Permitted	Permitted	Permitted
	Antihistamines, antileukotrienes (if prescribed for non-asthma condition)	Permitted	Permitted	Permitted	Permitted
	Methylxanthines/Theophyllines (if prescribed for non-asthma condition)	Permitted	Permitted	Permitted ¹	Permitted
	Mucolytics (not containing bronchodilators; stabilized 6 wks prior to V1)	Permitted	Permitted	Permitted	Permitted

1. Use rescue medication (salbutamol) delivered by each visit.
2. Commercial long-acting bronchodilators will be discontinued prior to Visit 2 in accordance with drug restriction for PFTs.
3. Patients on LAMA/LABA combination therapy (FDC or free dose combination) should be treated with either LAMA or LABA at Visit 0. Patients treated with LAMA or LABA monotherapy for at least 3 weeks are proceeded to Visit 1 and Visit 2.
4. SAMA is allowed to be used in patients who do not use any LAMA from Visit 0 until Visit 2.

Medication restrictions for pulmonary function testing

- At least an 8-hour washout of SABA bronchodilators.
- At least an 8-hour washout of SAMA bronchodilators prior to Visit 1 and 2 (Not allowed during treatment periods).
- At least a 48-hour washout of LABA (BID or QD) prior to Visit 1 and Visit 2 (Not allowed during treatment periods).
- At least a 48-hour washout of LAMA (BID or QD) prior to Visit 1 and Visit 2 (Not allowed during treatment periods).
- The morning dose of ICS should not be taken in the 1-hour period prior to PFTs.
- Morning doses of study medication should not be taken prior to test-day (Study medication should be taken on previous day of the visit)
- A patient visit may be re-scheduled twice due to lack of medication washout compliance.
- At least a 24-hour washout of short-acting (BID or more frequent administration) theophylline preparations.
- At least a 48-hour washout of long-acting (QD administration) theophylline preparation.

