5.2.2 Six-minute walk test (6MWT)

The test will be conducted according to the methodology described by ATS guideline ([R03-0725](#), [R13-4735](#), [R13-2807](#)). At Visit 1, a training for 6MWT before administration of 400 µg salbutamol will be done. At Visit 2, 6MWT for eligibility assessment will be performed before administration of the study medication. The 6MWT will be repeated at Visit 3 and Visit 4, starting 90 minutes (+15 minutes) after inhalation of the study medication.

During 6MWT, oxygen saturation and heart rate are monitored to measure [REDACTED] and recovery time for SpO₂ (%; see [Section 5.1.3](#)) using a mobile pulse oximeter, which is provided by BI.

[figure not shown]
During 6MWT and at the end of 6MWT, the intensity of breathing discomfort and leg discomfort will be assessed (modified Borg Scale as outlined in [Appendix 10.7](#)) by the patients. The outline of 6MWT is described in [Appendix 10.6](#).

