7.7 DETERMINATION OF SAMPLE SIZE

For the primary endpoint of IC at rest after Week 6, results from the recent two BI studies (BI no.:1237.13[[c02094185](#)] and 1237.14[[c02094318](#)]) suggest that the standard deviation is approximately 0.4[L]. However, a little conservative 0.41[L] is deemed more appropriate due to uncertain prediction of drop-outs during tests for physical activities. In addition the IC at rest after Week 6 is estimated at 0.1 L for the difference between tiotropium + Olodaterol (LAMA/LABA FDC) and tiotropium (LAMA). To detect a difference of 0.1 L with the standard deviation of 0.41 L in the IC at rest between the two treatments with 90% power at the 2-sided alpha of 0.05, 180 patients will be required. Nquery Advisor nTerim ver.2.0 (MOT0-1, 1-sample t-test) was used for the sample size calculation.

Table 7.7: 1 Summary of sample size considerations

primary endpoint	Δ [L]	SD [L]	N (power)
IC at rest[L]	0.1	0.41	180 (90%)
		0.40	171 (90%)

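### SAP 6.6 replaces a rescue-affected IC with the pre-treatment Visit 2 value under either treatment; the bias is probably small, but no planned analysis shows it

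*SAP*

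**What the plan says.** The spirometry rules in SAP 6.6 work in two steps. First, rescue on or before the measurement and "rescue use with unknown time will both result in all spirometry measurements for the visit being set to missing". Second, "In these cases the entire visit will be imputed with baseline". The same section limits rescue, for imputation purposes, to therapy for COPD symptoms needed at a clinic visit and entered on the rescue page of the eCRF. SAP 6.7 makes Visit 2 the common baseline for both periods.

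The Visit 2 spirometry comes before the first dose (Protocol 4.1.4 has the drug taken once the measurements are done). It follows "At least a 48-hour washout of LAMA (BID or QD) prior to Visit 1 and Visit 2", with the same interval for LABA (Protocol 4.2.2.1). Inhaled corticosteroid and other permitted background drugs continue.

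At Visits 3 and 4, FEV1 and FVC are taken 30 minutes after dosing and IC and SVC at 60 minutes (Flow Chart, footnote 11). The walk test follows, "starting 90 minutes (+15 minutes) after inhalation of the study medication" (Protocol 5.2.2). If rescue is needed on a test day, "the PFTs will be discontinued. The visit should be rescheduled if possible" (Protocol 4.2.1.1), and the clock time of rescue is recorded.

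Protocol 7.5 leaves completely missing visits to the model and defers imputation details to the SAP. The only other analysis of the primary endpoint in the visible text is the per-protocol run, done only if that set is below 90% of the FAS (SAP 6.3 and 7.4).

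**The concern.** Protocol 7.2 tests FDC against tiotropium. Imputing a pre-treatment value is a familiar device in a placebo-controlled trial. Here every patient receives tiotropium in both periods, so the Visit 2 value represents neither treatment, and a patient with one imputed visit no longer contributes an FDC-versus-tiotropium difference. The primary estimate then depends partly on how often rescue at the visit occurs under each treatment, and nothing planned isolates that dependence.

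Two details add to this.

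- **Unknown time.** Rescue may have followed a completed 60-minute IC, for example around the walk from 90 minutes. The rule would still delete that IC.
- **One measurement per visit.** The rule is justified by there being a single spirometry measurement at each on-treatment visit, but there are two time points. Rescue between them would also remove a valid 30-minute FEV1 and FVC, both secondary endpoints.

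**Working it through.** **Inputs from the documents.** Protocol 7.7 plans 180 patients, at a two-sided alpha of 0.05 and power of 90%, on these values: "To detect a difference of 0.1 L with the standard deviation of 0.41 L in the IC at rest between the two treatments". The method is a one-sample t-test, so 0.41 L acts as the SD of within-patient differences.

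**Inputs not in the documents (assumed).** tau, the tiotropium gain in IC over the Visit 2 value: 0.1 to 0.3 L. pT and pF, the shares of tiotropium and FDC visits imputed under the rule: 0 to 10%.

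**Step 1: reproduce the plan's figure.** Normal approximation: (0.41 × (1.960 + 1.282) / 0.1)² gives 177. Exact noncentral t gives 179, and power at 180 is 90.2%. With SD 0.40 L the exact result is 171, as the protocol states. The planned figure holds, and the planned standard error is 0.41/√180 = 0.031 L.

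**Step 2: effect on one patient.** With delta the true FDC-minus-tiotropium difference:

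- tiotropium visit imputed: expected difference delta + tau, so tau is added;
- FDC visit imputed: expected difference −tau, so tau + delta is removed;
- both imputed: difference exactly 0.

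**Step 3: effect on the estimate.** Expected estimate = (1 − pF)(delta + tau) − (1 − pT)tau = delta + pT·tau − pF·(tau + delta). The baseline covariate is common to both periods and cancels from the within-patient difference.

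Bias in litres, with delta = 0.1 L:

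| pT / pF | tau 0.1 | tau 0.2 | tau 0.3 |
|---|---|---|---|
| 5% / 5% | −0.005 | −0.005 | −0.005 |
| 5% / 2% | +0.001 | +0.004 | +0.007 |
| 5% / 0% | +0.005 | +0.010 | +0.015 |
| 10% / 5% | 0.000 | +0.005 | +0.010 |
| 10% / 0% | +0.010 | +0.020 | +0.030 |
| 0% / 5% | −0.010 | −0.015 | −0.020 |

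For example, at 5% / 2% and tau 0.2: 0.05 × 0.2 − 0.02 × 0.3 = +0.004 L, or 0.13 standard errors. With 180 patients, 5% is 9 visits.

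**Step 4: direction.** The bias favours FDC only if pT/pF > 1 + delta/tau. With delta = 0.1 L the threshold is 2.0, 1.5 and 1.33 at tau 0.1, 0.2 and 0.3 L. At equal rates p the effect is multiplied by (1 − p).

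**Step 5: false positives.** With delta = 0 the bias is tau(pT − pF). By normal approximation over the same range of tau, the two-sided error stays at 5.0% for equal rates, is 5.1 to 6.0% at 5% / 2%, and 5.3 to 7.8% at 10% / 5%. Only the extreme case (10% / 0%, tau 0.3 L) reaches about 16 to 17%. A simulation of 20,000 runs per scenario, using a period-adjusted paired analysis, agreed closely with the expected estimates and gave similar error rates in the scenarios run (for example 7.7% at 10% / 5% with tau 0.3 L).

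**Step 6: timing.** The order is FEV1/FVC at 30 minutes, IC/SVC at 60, walk from 90. Rescue at, say, 45 minutes leaves the 30-minute values untouched, yet the rule sets all spirometry of the visit to missing. Rescue known to follow the IC does not trigger the rule; rescue of unknown time always does.

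**The case against.** A reader might infer that the rule generally favours FDC. It does not. It applies equally to both treatments, and each imputed FDC visit removes more (tau + 0.1 L) than an imputed tiotropium visit adds (tau). Protocol 1.2 reports less daytime and night-time rescue on FDC than on the mono-components. That makes an imbalance plausible, but those are not clinic-visit data.

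Three other strong readings also fail.

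- **No look-back limit.** SAP 6.6 ties rescue to therapy needed at a clinic visit, so the window is already bounded.
- **A completed IC proves that rescue came later.** This is weak evidence only. Rescheduling depends on feasibility (Protocol 4.2.1.1), Protocol 6.1 provides for one rescheduling and then discussion, and code D1 in SAP Table 6.2: 1 anticipates improper washout at the primary-endpoint visits.
- **Visit 2 is drug-free.** It is pre-dose and off long-acting bronchodilators, while inhaled corticosteroid and other background treatment continue.

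The sponsor can also argue that baseline imputation after rescue matches the SAP's handling of discontinuation for worsening, and that treating rescue visits as missing at random is itself debatable. That stands: the choice is defensible and Protocol 7.5 allows it. Stopping and rescheduling tests, and recording clock times, should keep affected visits few. SAP 7.2 summarises pulmonary medication use during testing, but it does not count imputed visits or show their influence on the primary contrast.

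**Conclusion.** The point holds as a minor one. A visit imputed under SAP 6.6 contributes a pre-treatment value to a contrast between two active treatments, in either direction, and no visible analysis isolates the effect. With a few percent of visits affected the bias is small: +0.001 to +0.007 L at 5% versus 2%, at most about 0.23 of the planned standard error, and a slight shrinkage at equal rates. These sizes rest on assumed tau, pT and pF; the documents give none of them. The loss of a valid IC when rescue time is unknown, and of a valid 30-minute FEV1 and FVC when rescue falls between the two time points, follows from the wording, but its frequency is unknown and probably low.

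**What to change.** Before unblinding, amend SAP 6.6 and 7.4:

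1. Report the number of rescue-imputed visits by treatment, with unknown-time cases shown separately.
2. Add one sensitivity run of the primary model that leaves rescue-imputed visits missing and uses the observed IC where the rescue time is unknown.
3. Apply the rule separately to the 30-minute and the 60-minute measurements, so that rescue between them does not remove the earlier values.

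The primary analysis can otherwise stay as planned. The cost is a few sentences, one small table and one more run of the SAS code in SAP section 9. The downside is that the sensitivity run treats rescue visits as missing at random and may keep a few ICs affected by salbutamol, so it should be read beside the primary result and not in place of it.
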